Research on simulations for community nursing is somewhat sparse. Past studies have investigated the impact of home-visit simulation, high fidelity mannikin simulation, and standardized patients on improving the confidence, emotional intelligence, self-efficacy, empowerment, and stress management of nursing students (Hwang et al., 2020; Um, 2023; Ruiz-Fernández et al., 2022; Richards et al., 2010). However, these studies could not address the fundamental limitation of efficient teaching strategies for improved community nursing, primarily due to a lack of varied practice scenarios and overly hospital-centric circumstances, offering limited realism (Distelhorst & Wyss, 2013). A mixed-methods systematic review on the use of simulation practices in public or community health nursing revealed minimal simulation practices in public health nursing, suggesting a need for improvement (Aslan, 2021).

Technological advancements have led to the development of the Cave Automatic Virtual Environment (CAVE), a form of Virtual Reality (VR) that surpasses replicating real-world or

imagined environments and interactions with head-mounted VR displays. The emerging VR CAVE enhances environmental realism and immersion by projecting highly realistic environments onto surrounding walls (Abbas et al., 2024). The VR CAVE's strength lies in its ability to realistically emulate spacious environments, making it an ideal tool for practicing home assessments. This cost-effective and versatile training environment supports evidence-based and discovery-driven training, marking a significant advancement in community nursing education. A pilot study found that VR CAVE applications, which can recreate a broad range of household environments, are helpful and inspiring for the design of new technologies to support home care (Brennan et al., 2013). This could help overcome the limitations of the less versatile simulated home or VR simulation. However, no studies have used VR CAVE in community health nursing simulation for nursing student training. Further research is needed to confirm its efficacy and feasibility in enhancing their knowledge, self-confidence, satisfaction, and cultural competence. Therefore, this study aims to evaluate the outcomes and feasibility of applying VR CAVE simulation compared to a simulated home in community health nursing simulation for nursing students, with the goal of enhancing their knowledge, self-confidence, satisfaction, and cultural competence.

Objectives

The specific objectives of this project are:

1. To evaluate the effectiveness and feasibility of using the VR CAVE simulation in enhancing nursing students' knowledge and self-confidence in community health nursing;
2. To assess the impact of VR CAVE simulation on nursing students' satisfaction with their learning experience and their ability to provide effective care in community health settings;

3. To explore the potential of VR CAVE simulation in boosting the cultural competence of nursing students in community health nursing;
4. To compare the outcomes of VR CAVE simulation with those of traditional simulated home in terms of enhancing knowledge, self-confidence, satisfaction, and cultural competence in community health nursing among nursing student

Expected outcomes/ benefits/ deliverables

Nursing students will enhance their knowledge, self-confidence, satisfaction, and cultural competence in community health settings.

Primary outcomes

1. Nursing students will demonstrate a significant increase in knowledge and self-confidence in community health nursing following the application of VR CAVE simulation as compared to a traditional simulated home;
2. The use of VR CAVE simulation will enhance nursing students' satisfaction and cultural competence, improving their ability to transition from hospital-based care to community-based care.

Secondary outcomes

1. The VR CAVE simulation will serve as a model for the development of innovative, cost-effective, and versatile training environments that support evidence-based and discovery-driven training in community nursing education.
2. A comprehensive report detailing the effectiveness and feasibility of applying VR CAVE simulation in community health nursing education will be submitted for

presentation at a medical education/nursing conference and an international peer-reviewed publication.

3. The study will aid in the design protocol for a VR CAVE simulation model that can recreate a broad range of household environments, thus contributing to the advancement of teaching strategies in community health nursing education.

Statistical Analysis Plan

General Principles

All statistical analyses will be conducted using IBM SPSS Statistics version 28.0 (IBM Corp., Armonk, NY, USA). Statistical significance will be set at a two-sided $p < 0.05$. Continuous variables will be presented as mean and standard deviation (SD) or median and interquartile range (IQR) where appropriate, while categorical variables will be summarized as frequencies and percentages.

Analyses will follow the intention-to-treat (ITT) principle, including all participants as randomized regardless of protocol adherence. A per-protocol analysis may also be conducted as a sensitivity analysis.

Study Design Considerations (Crossover Structure)

This study adopts a two-period, two-sequence crossover randomized controlled design:

Sequence A: VR CAVE → Simulated Home

Sequence B: Simulated Home → VR CAVE

Each participant serves as their own control, improving statistical efficiency and reducing between-subject variability.

Key effects to be evaluated include:

Intervention (VR CAVE vs simulated home)

Period effect (first vs second session)

Sequence effect (order of intervention)

Carryover effect (residual effect from first intervention)

Outcome Measures

Primary outcomes:

Clinical competence (CCQ total and subscale scores)

Self-confidence and satisfaction (SSS scores)

Cultural competence (CCA total and subscale scores)

All outcomes are treated as continuous variables.

Baseline Analysis

Baseline characteristics (e.g., gender, prior clinical experience) will be compared between the two randomized sequences:

Categorical variables: Chi-square test or Fisher's exact test

Continuous variables: Independent samples t-test or Mann-Whitney U test (if non-normal)

This step assesses the success of randomization.

Primary Analysis

A linear mixed-effects model (LMM) will be used to evaluate intervention effects while accounting for repeated measures and crossover design.

Model specification:

Random effect: Participant ID

Fixed effects:

Intervention (VR CAVE vs simulated home)

Period (1 vs 2)

Sequence (A vs B)

Time (pre vs post)

Interaction terms (e.g., intervention \times time)

The primary parameter of interest is the intervention effect, estimated as the difference in outcome scores between VR CAVE and simulated home conditions.

Carryover Effect Assessment

To assess potential carryover effects:

A sequence effect will first be examined within the mixed model.

Additionally, an interaction term (intervention \times period) may be explored.

If a statistically significant carryover effect is detected ($p < 0.05$), analysis will be restricted to first-period data only, effectively treating the study as a parallel-group trial.

Within-Group and Between-Condition Comparisons

Pre–post changes within each condition will be analyzed using paired t-tests or equivalent model-based contrasts.

Between-condition differences (VR vs simulated home) will be derived from the mixed model estimates.

Handling Missing Data

Missing data will be assessed for patterns (missing completely at random, MCAR; missing at random, MAR).

Linear mixed models inherently accommodate missing data under MAR assumptions.

If necessary, multiple imputation will be performed as a sensitivity analysis.

Assumption Checking

Model assumptions will be evaluated:

Normality of residuals (Q-Q plots, Shapiro–Wilk test)

Homogeneity of variance

Linearity

If assumptions are violated, appropriate transformations or non-parametric alternatives will be considered.

Subgroup and Sensitivity Analyses

Where sample size permits, exploratory subgroup analyses may be conducted based on:

Prior clinical experience

Gender

Baseline competency levels

Sensitivity analyses:

Per-protocol analysis

First-period-only analysis (if carryover is present)

Effect Size Reporting

Effect sizes will be reported alongside p-values:

Mean differences with 95% confidence intervals (CI)

Standardized effect sizes (e.g., Cohen's d) where appropriate

Software and Reproducibility

All analyses will be conducted using SPSS v28. Syntax files and anonymized datasets will be retained to ensure reproducibility and auditability.

Project Plan

This project consists of the following four phases: 1) Preparatory phase -Developing two sets of VR CAVE community scenarios; 2) Briefing sessions; 3) Implementing the VR CAVE scenarios; and 4) Data analysis and generating design principles for VR CAVE model for community health nursing.

Phase 1: Preparatory phase

- Obtain HKU/HA HKW IRB.
- Inform and seek advice from Director of BN(FT) Program about the implementation of the project.
- Seek approval on using IAPCC-SV.
- Developing two sets of VR CAVE community scenarios
 - In this study, nursing students will use the VR CAVE to simulate home visits for two patients in a poverty home setting, Stone Wong and May Wong, each presenting unique health conditions and care needs. The VR CAVE will provide a realistic and immersive environment that replicates the patients' homes, complete with approximately twenty hidden cues in each case. These cues represent potential health hazards and cultural preferences related to health, challenging the students to observe, assess, and respond effectively.
 - Case 1 Summary: This case centers around Stone Wong, a 70-year-old man who was recently hospitalized due to difficulty in breathing. He was diagnosed with chronic obstructive pulmonary disease (COPD) with acute exacerbation. After

receiving various treatments, Stone showed clinical improvement and was discharged from the rehabilitation ward. As the assigned community nurse in this VR CAVE study, students are tasked with conducting an effective home visit to Stone. The objective is to identify potential health hazards in his home and understand his cultural preferences related to healthcare. Students are expected to demonstrate their knowledge and competency by conducting a respiratory assessment, providing education, and offering care tips for his Foley catheter. Approximately twenty hidden cues are present in the case to challenge the student's observational and assessment skills.

- Case 2 Summary: The second case involves May Wong, a 65-year-old woman who was hospitalized due to a persistent cough with a low-grade fever. She was diagnosed with pulmonary tuberculosis after her chest X-ray revealed extensive bilateral cavitary disease with mild bronchiectasis, and her sputum smears were positive for acid-fast bacilli. As May's assigned community nurse in this VR CAVE study, students are expected to conduct a thorough home visit. The aim is to identify potential health risks in her environment and understand her cultural health preferences. The primary outcome is for students to help May identify side effects of TB drugs and provide appropriate education. This case also includes around twenty hidden cues to stimulate the student's ability to observe, assess and respond effectively.
- Measuring tools:
 - **Demographics:** includes items such as gender, years of work experience and specialty

- **Clinical Competence Questionnaire (CCQ):** the 47-item Clinical Competence Questionnaire (CCQ) was utilized to assess the nursing students' perceived clinical competency. The CCQ consists of four competency areas: nursing professional behaviors, general performance, core nursing skills, and advanced nursing skills. Items were scored on a 5-point Likert scale, with the total score ranging from 47 to 235 - the higher the score, the higher the perceived competence. The CCQ demonstrated high reliability, with a Cronbach's alpha of 0.98 (Gu et al., 2018). (Appendix1)

- **Student satisfaction and Self-confidence in Learning (SSS):** SSB was prepared by the National League of Nursing (NLN, 2005). The survey was administered online using online Qualtrics, and consisted of 13 items that evaluated the participants' satisfaction with the instruction and their self-confidence in learning through the simulation. (Appendix 2)

- **Cultural Competence Assessment Instrument (CCA):** The CCA has 25 items in two subscales: cultural awareness and sensitivity and cultural competence behaviors. The instrument uses a 7-point response scale ranging from (1) strongly disagree to (7) strongly agree for the cultural awareness and sensitivity subscale and (1) never to (7) always for the cultural competence behaviors subscale. A higher score on the CCA indicates a higher level of cultural competence. The instrument's reliability and validity have been established (Doorenbos et al., 2003). For the study sample, Cronbach's alpha scores for the total CCA, cultural awareness and sensitivity subscale, and cultural competence behaviors subscale were 0.86, 0.70, and 0.90, respectively (Appendix3)

Phase 2: Briefing session

The project will be submitted to the Institutional Review Board of the University of Hong Kong for ethical approval.

All full-time Year 5 undergraduate nursing students (n=220) enrolled in the course Community & Global Health Nursing (NURS4604) will be invited to participate in this project. They are selected because Year 5 students must be equipped with fundamental knowledge about community health nursing, and must gain and expand clinical experiences and learn how to communicate and build relationships with the team, patients and their families.

The principal investigator will conduct a separate briefing session before the intervention at a mutually convenient time. This session will ensure that they understand all logistics and the knowledge required to guide the students through the cases in the study.

All participants will have a pre briefing time before the start of scenario. The principal investigator will explain the nature, purpose, procedures, risks and benefits of the proposed project to potential participants. Confidentiality and the voluntary nature of participation will be emphasized. Students who agree to participate will sign a consent form. The principal investigator will provide briefings on the project logistics and student expectations to ensure they are fully informed.

Then, students will be asked to take a pre-test and post-test on knowledge, self-confidence, satisfaction, and cultural competence in community health nursing.

Phase 3: Implementing the VR CAVE model

In the second semester, the VR CAVE model will be applied with Year 5 nursing students in the Community & Global Health Nursing (NURS4604) course. Students will form groups and actively participate in conducting home assessments and identifying health hazards for the patient with a play time of 20 minutes. In the proposed study, fifth-year nursing students will interact with a VR CAVE, a virtual reality environment designed to simulate home visits for two unique patients, Stone Wong and May Wong, both situated in a poverty-stricken home setting (Figure 1). With around twenty hidden cues in each case, the VR CAVE provides a realistic and immersive environment that mirrors the patients' homes. These cues symbolize potential health risks and cultural preferences related to health, thus challenging the students to observe, assess, and respond effectively.

Prior to the intervention, an online Qualtrics e-consent will be obtained from the participants. Furthermore, a pre-test will be conducted using the Clinical Competence Questionnaire (CCQ), Student Satisfaction and Self-confidence in Learning (SSS), and Cultural Competence Assessment Instrument (CCA). This will allow us to measure the baseline competencies of the students before the intervention.

The intervention group will then undergo the VR CAVE experience in Lab 1, while the control group will conduct a simulated home visit in the same lab. After completing the simulated home visit, the students will take an online Qualtrics post-test on the CCQ, CCA, and SSS. This will provide us with data to compare the competencies of the students post-intervention, and to assess the effectiveness of the VR CAVE as a training tool for nursing students.

Following the initial lab session, the two groups will switch settings for the second lab, thus ensuring a comprehensive and balanced assessment of the effects of the VR CAVE intervention.

The intervention group that initially experienced the VR CAVE will now shift to the

conventional simulated home, while the control group will have the opportunity to experience the VR CAVE intervention. This crossover design will provide a holistic view of the students' learning experience in both simulated environments.

Before the second lab session, participants will once again provide e-consent using Qualtrics. This reaffirms the ongoing voluntary nature of their participation. As in the first lab session, students will complete pre-tests using the Clinical Competence Questionnaire (CCQ), Student Satisfaction and Self-confidence in Learning (SSS), and Cultural Competence Assessment Instrument (CCA). This will allow us to monitor any changes in competencies as a result of the initial lab session.

After completing the second lab session, students will perform the same set of post-tests online via Qualtrics based on the CCQ, CCA, and SSS. This will enable us to evaluate any shifts in clinical, cultural, and satisfaction competencies following exposure to both the VR CAVE and the conventional simulated home. This comprehensive testing strategy will ensure that we capture a wide range of data to assess the overall effectiveness and impact of the VR CAVE technology in nursing education. The flow chart is shown in Figure 2.

Figure 1 VR CAVE model for poverty home

[figure not shown]

Figure 2 Flowchart of the study

Phase 4: Data analysis and generating design principles for a VR CAVE model

The primary and secondary analyses will involve descriptive statistics, including mean and standard deviation, to summarize participants' demographics and scores from the Clinical Competence Questionnaire (CCQ), Cultural Competence Health Practitioner Assessment (CCHPA-129), and Student Satisfaction and Self-Confidence in Learning (SSS). Baseline characteristics of the intervention and control groups will be compared using the χ^2 test or Fisher's exact test for categorical data and the independent t-test for continuous data. The CCQ, CCHPA-129, and SSS scores will be evaluated using a linear mixed-model analysis. Participants will be included as the random effect with time, group, randomization sequence order, and group x time interaction as fixed effects. The analysis will adhere to the intention-to-treat principle,

conducted on subjects as randomized. All statistical analyses will be performed using IBM SPSS version 28.0. All statistical tests will be two-sided with the level of significance set at 0.05.

Design principles specific to the context of the VR CAVE will be generated based on the findings of this project. These design principles will guide and be applied in further designing and developing VR CAVE for community health nursing.

Project schedule

Phase	Estimated Completion Time
1: Preparatory phase	January 2025
2: Briefing session	February 2025
3: Implementing the VR CAVE model	April-August2025
4: Data analysis and generating design principles for a VR CAVE model phase	January 2026

Reference

1. Thompson, C. W., Moscola, S., & Buckland, S. T. (2021). Nursing student perceptions of home visit simulation scenarios. *Nursing education perspectives*, 42(2), 113-114.
3. Alıcı, N. K., & Emiroğlu, O. N. (2020). Students' home visit experiences within the scope of public health nursing course: A qualitative study. *Acıbadem Üniversitesi Sağlık Bilimleri Dergisi*, 12(1), 146-151.
4. Dalton, J. M., Aber, C., & Fawcett, J. (2009). Students' perceptions of home visiting. *Home Healthcare Now*, 27(4), 253-261.
5. Meeley, N. G. (2021). Undergraduate student nurses' experiences of their community placements. *Nurse Education Today*, 106, 105054.

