Appendix 1 Clinical Competence Questionnaire

Nursing professional behaviors:

1. Following health and safety precautions
2. Taking appropriate measures to prevent or minimize risk of injury to self
3. Taking appropriate measures to prevent or minimize risk of injury to patients
4. Preventing patients from problem occurrence
5. Adhering to the regulation of patients' and families' confidentiality
6. Demonstrating cultural competence
7. Adhering to ethical and legal standards of practice
8. Maintaining appropriate appearance, attire, and conduct
9. Understanding patient rights
10. Recognizing and maximizing opportunity for learning
11. Applying appropriate measures and resources to solve problems
12. Applying or accepting constructive criticism
13. Applying critical thinking to patient cares
14. Communicating verbally with precise and appropriate terminology in a timely manner with patients and families
15. Communicating verbally with precise and appropriate terminology in a timely manner with healthcare professionals
16. Understanding and supporting group goals

Skill competencies:

17. Taking a history for new admissions
 18. Performing and documenting patient health assessment
 19. Answering questions for patients or families
 20. Educating patients or families with disease-related care knowledge
 21. Charting and documentation
 22. Developing care plan for patients
 23. Performing shift report
 24. Performing hygiene and daily care routines
 25. Providing rest and comfort measures
 26. Assessing nutrition and fluid balance
 27. Assessing elimination
 28. Assisting activities and mobility, and changing position
 29. Providing emotional and psychosocial support
 30. Performing venipuncture
 31. Starting intravenous injections
 32. Changing intravenous fluid bottle or bag
 33. Administering intravenous medications (or into intravenous bags)
 34. Administering intramuscular medications
 35. Performing subcutaneous (or intracutaneous) injection
 36. Administering oral medications
 37. Administering blood transfusion
 38. Performing urinary catheter insertion and care
 39. Performing sterile techniques
 40. Performing postural drainage and percussion, and oxygen therapy
 41. Performing preoperation/postoperation care
 42. Performing enema
 43. Performing upper airway suction
 44. Performing tracheotomy care
 45. Performing nasogastric tube feeding and care
 46. Performing chest tube care with underwater seal management
 47. Performing wound dressing care
-

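### Knowledge is claimed as a primary outcome, but no instrument in the plan tests it and the SAP's primary outcome list omits it

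*Combined protocol and SAP*

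**What the plan says.** Knowledge appears as an intended effect in several parts of the combined protocol and SAP:

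- The aim that closes the background names knowledge first among four things to be enhanced.
- Objective 1 refers to "enhancing nursing students' knowledge and self-confidence in community health nursing". Objective 4 compares the two settings on knowledge among other outcomes.
- The opening sentence under the expected outcomes says that students will improve in knowledge, and primary outcome 1 reads "Nursing students will demonstrate a significant increase in knowledge and self-confidence in community health nursing following the application of VR CAVE simulation".
- Phase 2 of the project plan says that "students will be asked to take a pre-test and post-test on knowledge, self-confidence, satisfaction, and cultural competence in community health nursing".

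The measurement and analysis sections name something else. The measuring tools under Phase 1 are a demographic form, the CCQ, the SSS and the CCA, and the CCQ is described as assessing "perceived clinical competency". Phase 3 gives the CCQ, SSS and CCA before and after each of the two lab sessions and mentions no other test. Under Outcome Measures, the first entry in the SAP's primary list is "Clinical competence (CCQ total and subscale scores"; the other two are the SSS and CCA scores. Phase 4 analyses the CCQ, the SSS and a cultural competence instrument under a different name (CCHPA-129), and again has no knowledge score.

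**The concern.** A primary outcome needs a measurement behind it. Here the first outcome named has none, although Phase 2 tells the reader that a test of it will be given before and after the sessions. A completed trial could report self-rated competence, satisfaction, confidence and cultural competence. It could not say whether students knew more after the VR CAVE than after the simulated home.

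The distinction matters more in this design because students necessarily know which setting they have just used. A self-rating can rise because an experience felt new or impressive, without any change in what the student knows. If the objectives keep the word while the data are self-ratings, the planned conference and journal report could draw a conclusion that the data cannot support. No analysis of the three questionnaires would repair that.

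**Working it through.** The plan has no figure to reproduce here. The check maps outcomes to instruments and then counts items.

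**1. Each claimed outcome against the instruments**

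| Outcome claimed in the objectives and primary outcomes | Instrument in Measuring tools and Phase 3 | In the SAP primary list |
|---|---|---|
| Knowledge | none | no |
| Self-confidence | SSS | yes |
| Satisfaction | SSS | yes |
| Cultural competence | CCA | yes |

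In the other direction, the CCQ heads the SAP list as clinical competence, but no objective names self-perceived clinical competence.

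**2. Could any item serve as a knowledge test?** Items visible in the appendices:

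- Appendix 1 (CCQ): 47 items, rated on a 5-point scale. The stated range agrees: 47 × 1 = 47 and 47 × 5 = 235.
- Appendix 2 (SSS): 13 items, rated 1 to 5. The instructions say that no answer is right or wrong.
- Appendix 3 (CCA): only the behaviour scale is visible, items 12 to 27, so 27 − 12 + 1 = 16 items.

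Total visible: 47 + 13 + 16 = 76. Items with a correct answer that could be scored: 0. The nearest is SSS item 8, which mentions acquiring required knowledge but asks how confident the student is of it. The CCA awareness and sensitivity items are not in the text available. Measuring tools describes them as rated from strongly disagree to strongly agree, which is not the format of a knowledge test.

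**3. Is knowledge scored anywhere else?** The case summaries under Phase 1 expect students to show knowledge through tasks such as a respiratory assessment, and each case has about twenty hidden cues. Neither the tasks nor the cues are defined as a scored outcome. Phase 1 also mentions approval to use an instrument labelled IAPCC-SV, but the plan does not describe it, schedule it or tie it to knowledge.

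**4. Side check: CCQ content against the two cases.** The summaries mention respiratory assessment, education, Foley catheter care, side effects of TB drugs, home hazards and cultural preferences. Items 30 to 47 are mainly procedures, for example "Performing chest tube care with underwater seal management".

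- Size of the block: 47 − 30 + 1 = 18 items.
- Leaving out oral medication (36), urinary catheter (38) and oxygen therapy (40), which touch the cases at least arguably: 18 − 3 = 15, and 15/47 = 32%.
- Also leaving out sterile technique (39) and wound dressing (47): 15 − 2 = 13, namely items 30–35, 37 and 41–46, and 13/47 = 28%.
- Score span: the total can move by 235 − 47 = 188 points. The 13 items carry 13 × 4 = 52 of them, the 15 items 15 × 4 = 60.

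If only the remaining items could respond, all by the same amount (an assumption), the difference in the total would be 34/47 = 72% or 32/47 = 68% of what it would be if every item responded. The effect on power cannot be worked out, because the plan gives no SD and no target difference.

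**The case against.** The strongest reply is that the SAP is already right. Its primary list names clinical competence, the SSS and the CCA and makes no claim about knowledge. The statements about knowledge sit under a heading that covers expected benefits and deliverables, where the secondary outcomes include a report and a design protocol, so they can be read as hopes rather than endpoint definitions. This stands in part: the analysis itself needs no change. It does not remove the mismatch, because Objectives 1 and 4 claim knowledge outright and Phase 2 promises a test of it.

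Three stronger readings are tempting, and the documents do not support them.

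- A reader might infer that the CCQ was chosen to stand in for knowledge and that its results will be reported as such. No section says so. The tool is openly labelled as perceived competency, and the risk of misreporting comes from the objectives' wording.
- A reader might take all 18 items in the 30-to-47 block (18/47 = 38%) as irrelevant hospital procedures. That is the size of the block, not the share missing from the cases. The appendix calls the items skill competencies, and nothing says that tasks such as wound dressing fall outside community nursing. Absence is also judged from short summaries, since the cues are not listed. The SAP already prespecifies CCQ subscale scores, so results need not rest on the total alone.
- A reader might state that no item in the full set of 85 (47 + 13 + 25) tests knowledge. Only 76 can be inspected; for the rest there is only the described response format.

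**Conclusion.** The point holds as an inconsistency between what the protocol claims and what it measures. Knowledge is asserted in the aim, two objectives, the expected-outcomes sentence, primary outcome 1 and the Phase 2 test description. No instrument described, administered or analysed is presented as a test of it, and the SAP does not list it. In size: one of the four constructs claimed, and the first named, has no data; 0 of 76 visible items test it. This assumes that the CCA items not shown follow their described agree/disagree format and that no further test exists outside these documents.

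Using self-ratings is a legitimate choice if they are called self-ratings. The CCQ content is a caution for interpretation only: 13 to 15 of 47 items are procedures that neither case summary mentions, which may dilute the total score but does not invalidate it.

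**What to change.** Replace knowledge with self-perceived clinical competence (CCQ) in the aim, Objectives 1 and 4, the expected-outcomes sentence, primary outcome 1 and the Phase 2 sentence on the pre-test and post-test. Use the same term in the planned report and draw no conclusion about knowledge. This matches the SAP, adds no data collection and remains possible after the sessions have been run. The cost is a narrower headline claim.

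Report the prespecified CCQ subscales next to the total. Appendix 1 shows only two headings although Measuring tools names four competency areas, so the SAP should state which items form each subscale.

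Optionally, the number of hidden cues found could be recorded as an observed secondary outcome at group level, because students work in groups. This is possible only if sessions remain to be run and both settings contain the same cues. The documents describe the cues for the VR CAVE and do not say whether the simulated home has them. If both conditions are met, the cost is a checklist for each session. If the simulated home would first have to be fitted with the same cues, the cost is higher.

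### About ten scores are primary, each tested at two-sided 0.05, and the plan has no multiplicity control and no rule for what counts as success

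*Combined protocol and SAP*

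**What the plan says.** The Outcome Measures section of the SAP puts three lines under primary outcomes: "Clinical competence (CCQ total and subscale scores"), "Self-confidence and satisfaction (SSS scores") and "Cultural competence (CCA total and subscale scores"). The subscales are therefore primary by the plan's own wording.

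The Measuring tools text in Phase 1 gives the structure of the instruments. On the CCQ: "The CCQ consists of four competency areas: nursing professional behaviors, general performance, core nursing skills, and advanced nursing skills". The SSS items "evaluated the participants' satisfaction with the instruction and their self-confidence in learning through the simulation", and Appendix 2 prints them under two headings. The CCA is described as having two subscales.

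On the significance level, General Principles in the SAP states "Statistical significance will be set at a two-sided" p below 0.05, and Phase 4 of the protocol states "All statistical tests will be two-sided with the level of significance set at 0.05". Neither section mentions an adjustment, a testing order, a lead score or a requirement that all scores succeed. Only the subgroup analyses are called exploratory.

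**The concern.** A 5% level for each test does not give a 5% level for a claim that can be reached through any of about ten tests. The protocol's own list of primary outcomes expects a significant gain over the simulated home in some constructs and an improvement in others. With nothing written about which scores carry those claims, the choice of score to report as the primary result can be made after the data are seen. A positive result on one CCQ area or one CCA subscale could then be presented as a primary finding, with a false-positive risk that the plan does not state.

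**Working it through.** The documents give no familywise error rate, sample size or power figure, so there is nothing of the plan's to reproduce. The only stated input is the per-test level, two-sided 0.05.

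**Step 1: count the primary scores.**
- CCQ: 1 total + 4 areas = 5 (Outcome Measures; Measuring tools)
- SSS: satisfaction and self-confidence = 2, or 3 if a total is also tested
- CCA: 1 total + 2 subscales = 3
- Sum: 5 + 2 + 3 = 10, or 11 with an SSS total
- Appendix 1 groups the CCQ items under only two headings. On that reading the CCQ gives 3 scores and the sum is 8 or 9.

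One VR CAVE versus simulated home contrast is counted per score.

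**Step 2: the limit for independent tests.** With no true effects, the chance of at least one false positive among k independent tests is 1 − 0.95^k:
- k = 8: 33.7%
- k = 9: 37.0%
- k = 10: 40.1%
- k = 11: 43.1%

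This limit cannot be reached here, because a total is the sum of its own subscales.

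**Step 3: allow for the structure of the scores.** Correlated test statistics were simulated (400,000 draws), with each total built as the equally weighted sum of its subscales. The correlations are assumptions; the documents give none.

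| Assumed correlation within / between instruments | 10 scores | 11 scores | 8 scores | 9 scores |
|---|---|---|---|---|
| 0 / 0 | 36.4% | 37.7% | 29.4% | 30.6% |
| 0.5 / 0.3 | 28.8% | 29.1% | 24.2% | 24.5% |
| 0.8 / 0.6 | 19.7% | 19.8% | 17.4% | 17.7% |
| 0.9 / 0.8 | 14.4% | 14.4% | 13.1% | 13.2% |

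For 10 to 11 scores the range is about 14% to 38%. The lowest figure in the table is 13.1%, and 13.1 / 5 = 2.6 times the nominal level.

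**Step 4: would it be enough to drop the subscales?** Three totals, each at 0.05 unadjusted, give 1 − 0.95^3 = 14.3% if independent and about 9% at 0.9 / 0.8. Fewer scores help, but an adjustment is still needed.

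**Step 5: check the proposed rule.** Four scores by Holm start at 0.05 / 4 = 0.0125. With no true effects and independent tests, the familywise error is 1 − (1 − 0.0125)^4 = 4.9%. Holm keeps it at or below 5% whatever the correlations.

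**Step 6: cost in power.** A test with 80% power at two-sided 0.05 has an expected z of 1.960 + 0.842 = 2.802. The critical value at two-sided 0.0125 is 2.498. Power there is Φ(2.802 − 2.498) = Φ(0.304), about 62%. The 80% is assumed.

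**The case against.** The strongest counter-argument is that the harm depends on a decision rule that the plan does not contain. A reader might infer that the SAP lets any one significant score prove VR CAVE better, but it does not say so. The protocol words its expected outcomes jointly and by construct. If every score had to succeed, familywise error would not be inflated; if each construct were a separate claim, 0.05 could be defended for each. This stands to the extent that the any-one-score reading must be labelled an assumption. It does not remove the gap. No joint-success rule is written, and a reading by construct still leaves five CCQ scores and three CCA scores at 0.05 each. If the four CCQ areas were uncorrelated, they alone would give 1 − 0.95^4 = 18.5%; correlation lowers this.

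The count can also be challenged. The SSS line does not say which scores are meant, Appendix 1 shows two CCQ headings against four areas in the text, and Phase 4 names the CCHPA-129 where the SAP names the CCA. So ten is provisional, but the 8-to-11 range leads to the same conclusion.

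Finally, this is a teaching study with feasibility and exploratory aims, and the SAP already asks for mean differences with 95% confidence intervals. That is a fair argument for a smaller confirmatory set. It does not support leaving all the scores primary at an unadjusted 0.05.

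**Conclusion.** The point holds. About ten scores are primary (8 or 9 if the CCQ has two parts), each at two-sided 0.05, with no adjustment, hierarchy or success rule. If any one significant score may be reported as meeting a primary outcome, the chance of at least one false primary result is about 14% to 38% for 10 to 11 scores. That range rests on assumed correlations running from none to 0.9 within and 0.8 between instruments. Still higher correlations would bring it closer to 5%.

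Two stronger readings are not supported. A reader might take 40% as the actual error rate, but that figure needs ten independent tests, and the totals are built from their subscales. A reader might also treat the CCQ total as the objectives' knowledge outcome. The objectives name knowledge, whereas the CCQ measures perceived clinical competence, and the plan has no separate knowledge test.

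**What to change.** Amend the SAP before any outcome data are analysed:

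1. Limit the confirmatory set to one score for each construct that the plan already treats as primary: CCQ total (described as perceived clinical competence), SSS self-confidence, SSS satisfaction and CCA total.
2. Name the single VR CAVE versus simulated home contrast to be tested for each. The primary model lists both an intervention term and, as an example, an intervention-by-time interaction, and Holm needs one defined p-value per outcome.
3. Test the four by Holm at an overall two-sided 0.05, with steps at 0.0125, 0.0167, 0.025 and 0.05.
4. Make the CCQ and CCA subscales secondary, reported as mean differences with 95% confidence intervals and without significance claims.
5. State the CCQ areas and the cultural instrument consistently across the SAP, Phase 4 and the appendices.

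This changes wording only. The cost is power: the smallest of the four p-values must be below 0.0125, where an outcome with an assumed 80% power at 0.05 has about 62%. The loss is smaller at later Holm steps, which are reached only after earlier rejections. A single primary score at 0.05, or the three totals at 0.0167 each, would also control the error, but each covers fewer separate claims.
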